#### 94 **Neural Cognitive Control Assessments:**

95 *EEG Recordings.* Neurophysiological data were recorded during each cognitive control assessment using an  
96 active two head cap (Cortech Solutions) with a BioSemiActiveTwo 64-channel EEG acquisition system in  
97 conjunction with BioSemiActiView software (Cortech Solutions). Signals were amplified and digitized at 1024 Hz  
98 with a 16-bit resolution. Anti-aliasing filters were used and data were band-pass filtered between 0.01–100 Hz  
99 during data acquisition. For each EEG recording session, a 1 × 1-inch white box was flashed for 10 ms at one of  
00 the corners on the stimulus presentation monitor at the start of each trial. A photodiode  
01 (<http://www.gtec.at/Products/Hardware-and-Accessories/g.TRIGbox-Specs-Features>) captured this change in  
02 luminance to facilitate precise time-locking of the neural activity associated with each sign event. During the  
03 experiment, these corners were covered with tape to prevent participants from being distracted by the flashing  
04 light.

05  
06 *EEG Preprocessing.* Preprocessing was conducted using the EEGLAB software. Noisy channels were identified  
07 upon initial visual inspection, were removed from the data, and interpolated using a spherical spline

08 interpolation, using the average signal of the surrounding channels to reconstruct the data in the removed  
09 channel. The data were then down-sampled to 1024 Hz to reduce the computational demand without losing  
10 any important information in the data. A finite impulse response filter with a high-pass cutoff of 1 Hz was applied  
11 to remove drift, and then a low-pass filter at 40 Hz was applied to remove high frequency noise. Ocular  
12 correction was performed by using ICA to isolate and remove activity induced by eye-blinks and lateral eye  
13 movements from the signal. The data were then re-referenced to the average signal of all channels. Epochs of -  
14 1000 ms to +1000 ms were generated for each stimulus type for subsequent analyses. Epochs containing  
15 excessive peak-to-peak deflections ( $\pm 100 \mu\text{V}$ ) were removed.

16

17 *Midline Frontal Theta Analyses.* Midline frontal theta (4-7Hz) power (mft Power) has been implicated in  
18 sustained attention abilities, including correlating with RTV across the lifespan, that can evidence the  
19 engagement of the prefrontal cognitive control processes during a given task. This particular marker has also  
20 demonstrated a level of sensitivity in revealing changes following a digital intervention in multiple  
21 studies. Time series were created by resolving 4-40 Hz activity using a fast Fourier transform (FFT) in  
22 EEGLAB in epochs from -1000 to +1000msec. Midline frontal theta total power analyses (evoked power +  
23 induced power) across trials from the vigilance task was conducted by resolving 4–40 Hz activity using a fast  
24 Fourier transform in EEGLAB, with these values subsequently referenced to a -900 to -700 pre-stimulus baseline  
25 (thus relative power (dB)). After mft relative power was computed, we specifically interrogated a predetermined  
26 cluster of frontal electrodes (Fz, FPz, AF3, AF4, and AFz) at the time window of maximum power, as this is the  
27 same approach that we have previously utilized in several intervention studies interrogating mft power  
28 changes.

29

### 30 **Physical outcome measures:**

31 To capture changes in physical fitness due to training during the study, all participants underwent a  
32 comprehensive physical outcomes assessment in addition to the cognitive assessments described above. Our  
33 targeted outcome measures were a senior-specific measure of stability indicative of fall risk as well as a  
34 physiological measure of fitness and health (diastolic blood pressure). Our decision to focus on diastolic (rather  
35 than systolic) blood pressure was based on diastolic blood pressure being a proportionally larger contributor to  
36 mean arterial pressure (MAP), with MAP being an important predictor of cardiovascular disease.  
37 Descriptions of each exploratory fitness measure evaluated, including systolic blood pressure, are described in

38 the **Supplemental Materials**; note that these measures came from the Senior Fitness Test (SFT) to assess global  
39 physical performance.

40  
41 **Training-related expectancy ratings:**

42 In an effort to identify an expectancy matched placebo versus the BBT intervention, we first compared  
43 expectancy on 10 different apps to BBT in a sample of 261 participants (Female=135, mean age=33.5). Each  
44 participant was randomly assigned to view a video of BBT or one of 10 potential apps (n= 15–30 individuals  
45 per app) which we did not hypothesize would improve cognitive abilities. They were then asked to rate the  
46 extent to which the presented intervention would lead to improvements on these outcomes, using a Likert  
47 scale measuring 1 (no improvement) to 7 (a lot of improvement). Following this first round of testing, we  
48 selected the three apps that had the highest expectancy matching scores, and subsequently collected new  
49 expectancy data in a sample of 76 young adults to assess the level of expectancy involving the combination of  
50 these three apps (n=37) versus BBT (n=39). Here we found no differences in participant expectations of  
51 improvement on our CPT task ( $t_{74}= 0.24$ ,  $P = 0.62$ , 95% CI: -1.3 to 0.77) or on our filter task ( $t_{74}= 0.55$ ,  $P = 0.16$ ,  
52 95% CI: -0.30 to 1.8), suggesting that we had comparable expectancy on this battery of control apps as  
53 compared to the BBT intervention with respect to our cognitive control outcome measures.

54 To determine if these expectancy findings held with older adults, we had 91 older adults complete this same  
55 expectancy survey. These older adults were shown a recording of either the BBT (n=46, mean age=64.4, Female=28) or  
56 the MBT (n=45, mean age= 63.2, Female=31) interventions and subsequently shown a video describing our cognitive  
57 outcome measures. We observed no significant difference between interventions in terms of participant expectations of  
58 improvement on the CPT (independent t-test:  $t_{89} =-1.84$ ,  $p=0.069$ , with the MBT intervention showing a trend towards  
59 having greater expectation of improving on this measure than the BBT group) and the Filter tasks (independent t-test:  $t_{89} =-0.682$ ,  $p=0.50$ ). To ensure that these findings extended to the present study, we asked all BBT and MBT participants to  
60 complete a comparable version of this survey after they had completed their first few days of training on their assigned  
61 intervention to see if their experience led to different expectancy-based perceptions. This was motivated especially by  
62 the fact that the MBT training experience was distinct from the BBT training experience in that they completed their  
63 training at home on a tablet by themselves, whereas the BBT group trained at a laboratory on a large screen TV in the  
64 presence of a trainer. Once again, we observed no significant difference between interventions in terms of participant  
65 expectations of improvement on the CPT (independent t-test:  $t_{36} =1.26$ ,  $p=0.21$ , MBT mean=5.0, BBT mean=5.4) and the  
66 Filter tasks (independent t-test:  $t_{36} =0.64$ ,  $p=0.53$ , MBT mean=5.0, BBT mean=5.3).  
67  
68

Statistical Analysis Approach

IRB 10-04957

A video game to enhance cognitive health in older adults, children, and adolescents

“Characterizing the Synergistic Effects of Physical and Cognitive Training on Attention and Working Memory”

May 31 2023

Statistical Analysis Approach:

Analyses were conducted by researchers who were blind to group membership. To test for training effects on each of the collected outcome measures, we used an repeated measures ANOVA approach as in our previous work^{1,2}. Statistically, no between-group differences assessed using independent t-tests were observed for at baseline involving: (1) age ($t_{47}= 0.35$, $p= 0.73$); (2) gender ($t_{47}= -0.15$, $p= 0.88$); (3) CPT performance ($t_{45}= 1.84$, $p= .07$); (4) Filter task performance ($t_{46}= 1.34$, $p= .19$); (5) mft power ($t_{44}= 1.70$, $p= .10$); (6) mft ITC ($t_{41}= 1.11$, $p= .28$); (7) limits of stability ($t_{44}= 1.05$, $p= .30$); (8) diastolic blood pressure ($t_{43}= 1.77$, $p= .08$). For those measures that showed a trend towards a group difference at baseline (CPT performance, mft power, and blood pressure), we performed an analysis of covariance (ANCOVA) with post-training performance as the dependent variable, pre-training performance as the covariate, and group as the fixed factor. Our reasoning for using this approach is that this analysis accounts for variation around the post-test means that arises from the variation where participants began at pretest³. Using this approach, we observed a nearly significant group difference following training for the CPT task ($F_{(1,46)}= 3.85$, $p=0.056$), a significant group effect for mft power ($F_{(1,44)}= 4.35$, $p=0.043$) and a significant group effect for diastolic blood pressure ($F_{(1,42)}= 6.93$, $p=0.012$), supporting the assertion that the reported ANOVA effects were not driven by trending baseline differences between groups. For post-hoc analysis of the within-group changes, we performed two-tailed, paired-sample t-tests on each group separately to test for significant differences between each testing session. We report Cohen's d for all significant ($p< .05$) and trending ($p< .10$) ANOVA results, using the Hedges and Olkin correction⁴ for small sample bias.

References

- 1 Anguera, J. A. *et al.* Video game training enhances cognitive control in older adults. *Nature* **501**, 97-101, doi:nature12486 [pii] 10.1038/nature12486 [doi] (2013).

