## 26 METHODS

### 27 Participants:

28 The study was approved by the Committee on Human Research at the University of California, San Francisco, and  
29 retrospectively registered on ISRCTN registry [ISRCTN [66423499] to distinguish the goals and approach taken here from  
30 those of the 'parent' registration (clinicaltrials.gov submission NCT03032796). This study was designed to gauge the  
31 feasibility and potential efficacy of using the BBT intervention compared to an expectancy matched active placebo  
32 group, for a subsequent mechanistic trial exploring synergistic effects of a combined intervention versus individual  
33 components alone (as described in the 'parent' clinicaltrials.gov submission). For continuity and cohesion, we used the  
34 same primary (CPT) and secondary (Working Memory Task) outcome measures listed in the parent clinicaltrials.gov  
35 registration. Furthermore, here we also examined a subset of the exploratory outcomes listed in the parent registration  
36 (blood pressure, event-related spectral perturbation derived from EEG) as well as two new exploratory measures (Filter  
37 Task, Limit of Stability Assessment). 49 healthy, older adult (OA) individuals consented to participate in this study. OAs  
38 were randomly assigned (block size of 5) to a training group (body-brain trainer; BBT; N=24, mean age=68.8 +/- 5.9, 13  
39 females) or an active, expectancy-matched control group (mind-body trainer; MBT; N=25, mean age=68.20 +/- 6.75, 13  
40 females). All participants were from the San Francisco Bay Area and recruited through online and newspaper  
41 advertisements. All participants had normal or corrected-to-normal vision, had no history of stroke, traumatic brain  
42 injury, or psychiatric illness, were not taking psychotropic, hormonal, or cardiovascular medications, and did not have  
43 any physical or mental conditions that may interfere with their daily activities (e.g., migraine headaches, substance  
44 abuse, neuropathy). Similar to our previous work, all participants reported playing less than 2-hours of video games per  
45 month, and completed a general health questionnaire reviewed by the study team assessing each individual's current

46 state of physical fitness to ensure that they could safely engage with the physical aspects of the BBT platform. All  
47 participants gave written informed consent, and were paid \$15/hour for their in-lab and at-home participation. All  

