91 and other support during the training.

92 All participants reported to our UCSF Neuroscape laboratories prior to training ('Pre-training' session) and  
93 following the completion ('Post-training' session) of training (1-week grace period from start/end of training) to compete  
94 a battery of cognitive and physical outcome measures to assess training-related changes. Participants were invited to  
95 return to the laboratory 1 year after their post-training outcome assessment to evidence which, if any, positive training  
96 effects persisted in the cognitive domain. Over the course of the study, 3 participants in the BBT group and 2  
97 participants in the MBT group voluntarily withdrew from the study, resulting in the complete pre- and post-training data  
98 sets from 24 BBT participants and 25 MBT participants. One additional participant had a non-training related adverse  
99 event which caused them to withdraw from the study prior to be randomized to a group. We were unable to collect EEG  
00 data from three participants at pre-training due to equipment malfunctions, and, due to technical issues with  
01 photodiodes, we were unable to time-lock the EEG to the event onsets for several other participants (n= 4 at pre-  
02 training, n= 4 at post-training). There was one participant who did not return for their post physical assessment.

#### 03

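### The stated ANOVA and ANCOVA use only people with every modelled session, and no model is given for 1-year persistence; a mixed model would keep all sessions, with a small precision gain for EEG and a safer 1-year answer

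*SAP*

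**What the plan says.** The SAP (Statistical Analysis Approach) names one main method for training effects on every outcome: "we used an repeated measures ANOVA approach as in our previous work". For CPT, midline frontal theta (mft) power and diastolic blood pressure it adds an ANCOVA "with post-training performance as the dependent variable, pre-training performance as the covariate, and group as the fixed factor". Within-group change is examined by "two-tailed, paired-sample t-tests on each group separately to test for significant differences between each testing session", without naming the sessions. It contains no missing-data rule, no mixed model and no sentence on how the 1-year data are analysed.

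The protocol (Study Design) shows that sessions are missing. The team could not collect EEG "data from three participants at pre-training due to equipment malfunctions", and photodiode faults prevented time-locking for other participants, 4 at pre-training and 4 at post-training. On the 1-year visit the text runs "a battery of cognitive and physical outcome measures to assess training-related changes. Participants were invited to", followed by the return to the laboratory a year after the post-training assessment. No return count is given. The same section reports 5 voluntary withdrawals (3 BBT, 2 MBT) and describes the 24 + 25 analysed as the complete pre/post sets. The protocol's introduction lists 1-year persistence among the secondary questions, and its opening list of procedures and time commitments includes the 1-year assessment.

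**The concern.** A classical repeated-measures ANOVA drops anyone who lacks a session that is in the model, and the ANCOVA drops anyone without both values. A participant with a usable post-training EEG but no pre-training EEG therefore contributes nothing.

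For the 1-year question there are two possibilities, and the SAP does not say which applies:

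- If 1-year data are analysed separately, the answer describes returners only.
- If three sessions enter one ANOVA, non-returners are also removed from the pre/post contrast.

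At stake are some precision on the EEG outcomes and the trustworthiness of a named secondary answer.

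**Working it through.** **1. Reproduce the reported results.** Tail areas from the SAP's F values and degrees of freedom:

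- CPT, F(1,46) = 3.85: p = 0.0558 (stated 0.056)
- mft power, F(1,44) = 4.35: p = 0.0428 (stated 0.043)
- Diastolic pressure, F(1,42) = 6.93: p = 0.0118 (stated 0.012)

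All three agree.

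**2. Numbers of people implied.** A two-sample t-test has n = df + 2. A one-covariate, two-group ANCOVA has n = error df + 3; df + 2 is shown as a lenient variant.

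| Outcome | Baseline t-test n | ANCOVA n (df+3 / df+2) | Stated EEG losses leave |
|---|---|---|---|
| CPT | 45 + 2 = 47 | 49 / 48 | not applicable |
| mft power | 44 + 2 = 46 | 47 / 46 | 42 pre, 45 post |
| mft ITC | 41 + 2 = 43 | none reported | 42 pre, 45 post |
| Diastolic pressure | 43 + 2 = 45 | 45 / 44 | not applicable |

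The CPT ANCOVA contains more people than had a baseline value under either convention. The mft power counts exceed the 42 pre-training recordings that the protocol's losses allow. Only ITC is close.

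**3. Complete EEG pairs, if all stated losses fall among the 49.** Pre-training: 49 − 3 − 4 = 42. Post-training: 49 − 4 = 45.

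- Photodiode losses in eight different people: 49 − 3 − 8 = 38 pairs, and 45 − 38 = 7 people with post-training only.
- Photodiode losses in the same four people: 49 − 3 − 4 = 42 pairs, and 45 − 42 = 3 people with post-training only.

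The loss is 7/49 = 14% to 11/49 = 22%.

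**4. Gain from keeping post-only people.** With a common baseline mean, a complete pair carries information 1/(1 − r²) on the post-training arm difference and a post-only person carries 1, where r is the pre/post correlation (assumed). The ratio of standard errors (all sessions to complete pairs) is √[A/(A + m)], with A = pairs/(1 − r²) and m the post-only count.

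- 38 pairs, m = 7: r = 0.4 gives √(45.24/52.24) = 0.931; r = 0.7 gives √(74.51/81.51) = 0.956. Reduction 6.9% to 4.4%.
- 42 pairs, m = 3: r = 0.4 gives √(50/53) = 0.971; r = 0.7 gives √(82.35/85.35) = 0.982. Reduction 2.9% to 1.8%.

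The full range is about 2 to 7%. For a group-by-time contrast without the common baseline the reduction is 0.2 to 4.7% (r from 0.9 to 0.3).

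**5. 1-year precision (return rate assumed, 50 to 90%).** If three sessions were modelled jointly, the pre/post standard error would exceed that with all 49 by √(1/0.9) − 1 = 5% up to √(1/0.5) − 1 = 41%. At 34 of 49 returning it would be √(49/34) − 1 = 20%. For the pre-to-1-year contrast itself, a mixed model lowers the standard error by only 2 to 9% (correlation 0.5 to 0.7), because it cannot recreate missing 1-year values.

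**6. 1-year bias (illustration).** A simulation used unit SDs, no true change, correlations of 0.6 (pre/post), 0.5 (pre/1-year) and 0.6 (post/1-year), and about 60% return. The figures are bias in one arm's mean pre-to-1-year change.

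| Return depends on | Returners only | Mixed model |
|---|---|---|
| Observed pre-to-post change | 0.17 SD | about 0 |
| Unseen 1-year value | 0.16 SD | 0.21 SD |

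Bias in the arm difference is the difference between the two arms' biases, so it is smaller if selection acts alike in both.

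**The case against.** The strongest reply is that this is mainly a reporting gap in a feasibility study.

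- **The EEG gain is small.** For an effect with 80% power at n = 49, power is 69 to 73% with complete pairs and 70 to 74% with a mixed model for the group-by-time contrast. This stands.
- **The EEG set is not self-selected.** A reader might infer that it is, but the protocol attributes every loss to equipment or photodiodes and documents no selection mechanism.
- **Complete-case analysis does not always need data missing completely at random.** A correctly specified ANCOVA stays valid when missingness depends only on arm and baseline. This stands for the three ANCOVA outcomes at post-training. It does not cover 1-year return, which may also depend on the post-training result.
- **The reported counts do not show the drop.** mft power has 46 to 47 people, a loss of 4 to 6% of 49. EEG was recorded during each cognitive assessment (protocol, EEG Recordings), so the listed losses need not all fall on CPT theta. This makes step 4 conditional. It does not rescue the plan, because a post-on-pre ANCOVA cannot hold more people than have baselines.
- **Nothing shows that the pre/post results were cut to returners.** A reader might take the 20% figure as a loss that occurred. No text says three sessions were modelled together, and the ANCOVA counts of 44 to 49 do not suggest it.
- **"Volunteers only" would overstate the 1-year set.** The visit was scheduled and participants were invited to it. That those who benefited return more often is plausible but not documented.
- **Replacing the main model now would be a choice made after seeing results.** This stands and shapes the remedy.

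**Conclusion.** The point holds in a limited form. The stated methods need every modelled session, and the 1-year question has no stated model, so its answer would rest on returners.

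For EEG the cost is precision: about 2 to 7% of the standard error, provided that the stated losses fall among the 49, the pre/post correlation is 0.4 to 0.7 and losses are similar by arm. At 1 year the size of any bias is unknown because no return rate is given; the 0.17 SD figure is an illustration. A mixed model removes bias from return that depends on observed results. It does not help, and may do slightly worse, if return depends on the unseen 1-year value.

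The analysis set still matters. At a fixed estimate, a 3.5% larger standard error would take mft power past 0.05 (√(4.35/4.06) = 1.035), and a 2.5% smaller one would bring CPT to it (√(3.85/4.05) = 0.975). That is a reason to settle who is analysed, not to seek either result. The documents do not support the reading that the reported pre/post findings are biased by selective dropout from the ANOVA.

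**What to change.** 1. **Reconcile first.** Report n by arm, outcome and session, and the 1-year return count. Resolve mft power (46 to 47 against 42) and CPT (48 to 49 against 47). Settle also whether the 5 who withdrew are additional to the 49: the protocol says "49 healthy, older adult (OA) individuals consented to participate in this study" but gives the same total as complete after the withdrawals. If they are additional, 54 were randomised and 5/54 = 9.3% are left out.
2. **Fit a linear mixed model per outcome.** Use pre, post and, for cognitive outcomes, 1-year sessions, with session-by-arm terms, a common baseline mean, unstructured covariance, REML and Kenward-Roger degrees of freedom. Include every randomised participant with any session, including those who withdrew if they have data. Read the arm differences at post-training and at 1 year from this model.
3. **Label it post hoc** and present it beside the ANOVA and ANCOVA, since those results are already reported.
4. **Add a missing-not-at-random sensitivity analysis at 1 year**, for example shifting the unobserved values by arm over a stated range.

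The cost is a modest re-analysis in standard software and a paragraph in the SAP. The drawback is that the model relies on data being missing at random, which step 4 probes but cannot verify.

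### The participant counts implied by the SAP's frontal-theta power tests (46 at baseline, 47 in the ANCOVA) do not agree with the EEG losses reported in the protocol

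*SAP*

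**What the plan says.** **Protocol, Study Design.** After withdrawals ("3 participants in the BBT group and 2" in MBT), the protocol reports complete pre- and post-training data "sets from 24 BBT participants and 25 MBT participants", which is 49 people. It then says EEG could not be collected for some: "data from three participants at pre-training due to equipment malfunctions". A second group is separate from these: "we were unable to time-lock the EEG to the event onsets for several other participants (n= 4 at pre"-training, and a further n = 4 at post-training. The section does not say whether the affected people are among the 49, which task was affected, or what was done with the recordings.

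**Protocol, Neural Cognitive Control Assessments.** The photodiode captured the change in screen "luminance to facilitate precise time-locking of the neural activity associated with each sign event". Epochs run from 1000 ms before to 1000 ms after each stimulus. Theta power comes from the vigilance task and is referenced to a window 900 to 700 ms before the stimulus.

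**SAP, Statistical Analysis Approach.** The age comparison, "1) age ($t_{47}= 0.35$, $p= 0.73", uses all 49. The theta comparisons are "5) mft power ($t_{44}= 1.70$, $p= .10$); (6) mft ITC ($t_{41}= 1.11$, $p= .28". The power ANCOVA, with the pre-training value as covariate, is F(1,44) = 4.35, p = 0.043.

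**The concern.** Power measured in a stimulus-centred epoch against a pre-stimulus baseline needs to know when the stimulus appeared. A recording that could not be locked to event onsets should therefore not contribute a value. Yet the baseline power test has the number of people left when only the three without any EEG are removed, and the ANCOVA, which needs both sessions, has one more than that.

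The result matters to the argument. The neural mechanism is one of the protocol's stated secondary questions. The SAP uses the power ANCOVA, one of its two significant ANCOVA results, to argue that the reported effects were not driven by baseline differences. Its p-value is close to 0.05, so which people are in the analysis could decide how it reads.

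**Working it through.** **Inputs.** From the protocol's Study Design section: 24 + 25 = 49 complete data sets; 3 + 2 = 5 withdrawals; 3 with no pre-training EEG; 4 others unlocked at pre-training; 4 unlocked at post-training. From the SAP: t with 44 df (power), t with 41 df (ITC), F(1,44) for the power ANCOVA. For comparison: CPT t with 45 df and F(1,46); diastolic pressure t with 43 df and F(1,42).

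**Step 1: reproduce the SAP's p-values at its own df.**
- Power baseline: t = 1.70 on 44 df gives p = 0.096 (stated .10).
- ITC baseline: t = 1.11 on 41 df gives p = 0.274 (stated .28).
- Power ANCOVA: F = 4.35 on (1,44) gives p = 0.0428 (stated 0.043).

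These p-values do not help to identify the true n. At 40 df the two baseline values would be 0.097 and 0.274.

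**Step 2: number of people implied by the df.** For a two-group t-test, N = df + 2. A Welch df would imply an equal or larger N. For an ANCOVA with two groups and one covariate, N = error df + 3.

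| Measure | Baseline N | ANCOVA N |
|---|---|---|
| Theta power | 44 + 2 = 46 | 44 + 3 = 47 |
| ITC | 41 + 2 = 43 | none reported |
| CPT | 45 + 2 = 47 | 46 + 3 = 49 |
| Diastolic pressure | 43 + 2 = 45 | 42 + 3 = 45 |

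The power ANCOVA exceeds its own baseline N by one. The CPT ANCOVA, where EEG plays no part, exceeds its own by two. Diastolic pressure agrees.

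**Step 3: number available, if all losses are among the 49 and affect the vigilance task.**
- Any pre-training EEG: 49 − 3 = 46.
- Event-locked pre-training EEG: 46 − 4 = 42, so at most 40 df for a baseline test.
- Event-locked at both sessions: 42 if the four post-training losses are the same people as the four at pre-training, 42 − 4 = 38 if they are different people. Error df = 42 − 3 = 39 down to 38 − 3 = 35.

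Baseline power (46) is 4 above 42. The power ANCOVA (47) is 5 above the largest number of pairs. ITC (43) is 1 above 42.

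**Step 4: allow for losses among the withdrawals.** If k of the seven pre-training losses were among the five people who withdrew, the locked pre-training count within the 49 is 42 + k, a range of 42 to 47. Baseline power then needs k = 4 and ITC needs k = 1, or k = 4 with three further ITC exclusions.

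This does not rescue the ANCOVA. People with a post-training recording that failed to lock attended post-training, so they are naturally read as completers. They alone limit the pairs to 49 − 4 = 45, or 45 − 3 = 42 error df, wherever the pre-training losses fell. Even if the printed error df were N − 2, N would be 46, still above 45.

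**Step 5: sensitivity of the ANCOVA p-value.** As an illustration only, hold the effect size fixed and scale F with the error df, F = 4.35 × df / 44:

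| Error df | F | p |
|---|---|---|
| 44 (SAP) | 4.35 | 0.043 |
| 42 | 4.15 | 0.048 |
| 39 | 3.86 | 0.057 |
| 35 | 3.46 | 0.071 |

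A real re-analysis would change the estimate as well as the df.

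**The case against.** A reader might infer that unlocked recordings were analysed, because 46 is exactly 49 − 3. The documents do not establish this. Without event times there are no stimulus epochs to cut, so inclusion is not an obvious thing to have happened, and nothing in either document says it did. Misreported df are as plausible: the CPT shows the same fault, an ANCOVA larger than its own baseline test, with no EEG involved. Recovered recordings, imputation that is not described, or an error in the protocol's counts are also possible. This part of the objection stands.

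Four further points also stand.
- The figure of 42 is conditional. Study Design does not say that the seven pre-training losses are among the 49, and EEG was recorded in every cognitive control assessment, so the lost lock may not concern the vigilance task.
- For the same reason it cannot be said that at least four of the 46 baseline values are invalid. With k = 4 the number is zero.
- The ITC excess is one person. Nor are 46 and 43 incompatible, since ITC may have had exclusions of its own; the documents do not describe how it was computed.
- The protocol classes the EEG spectral measure as exploratory, and the baseline p-values hardly depend on the df.

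The objection does not remove the conflict for power. Placing pre-training losses among the withdrawals can reach 46 at baseline, but cannot produce 47 pairs when four post-training recordings were not locked.

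**Conclusion.** The theta-power counts in the protocol and the SAP do not agree. If all the losses are among the 49 and affect the vigilance task, the excess is 4 people at baseline (46 against 42) and 5 to 9 in the ANCOVA (47 against 42 to 38). On the reading most favourable to the SAP, with only the post-training losses counted, the ANCOVA excess is still 2 people (47 against 45; error df 44 against 42). That bound assumes that the four post-training losses are among the completers and concern the vigilance task.

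The cause is open: unlocked recordings in the analysis, misreported df, or wrong counts in the protocol. Each would need a correction or a disclosure. The finding concerns power. The ITC count needs an explanation but is not evidence of a fault.

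**What to change.** 1. Confirm, for each participant and session, whether a vigilance-task EEG recording exists and has a valid event lock, and whether the person is among the 49.
2. Restrict the power baseline test to people with a valid pre-training recording, and the power ANCOVA to those valid at both sessions. Re-run both.
3. Report the corrected df and p-values, with n by arm and session beside each result.
4. State how unlocked recordings were handled and why the ITC count differs from the power count.
5. Correct the protocol's Study Design section or the SAP, whichever is wrong, so that they agree.

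The cost is a check of the session records, two re-run analyses and a few lines of text. If the check shows that only the df were misprinted, the work ends with a correction. The downside is that the theta p-value of 0.043 may move either way, and the SAP's argument about baseline differences would have to follow it.
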